7.1 NULL AND ALTERNATIVE HYPOTHESES

Throughout this Section, alteplase refers to the randomised treatment group, which is in addition to SOC. With regards to Part 1, reference will be made to alteplase dosing regimen A and alteplase dosing regimen B and in Part 2, reference will be made to alteplase.

The primary endpoint related to Part 1, secondary endpoints, [REDACTED] will be evaluated in an exploratory manner.

For Part 2:

The primary objective of the statistical analysis is to determine whether alteplase significantly increases the chances of clinical improvement or hospital discharge up to Day 28, in comparison to SOC alone. The key secondary objectives of the statistical analysis are to determine whether alteplase significantly prevents treatment failure (defined as WHO value \geq 7) at Day 28, or all cause mortality at Day 28, in comparison to SOC alone.

For the primary analysis of the primary endpoint a Cox proportional hazards model will be used. In the NIV patient cohort, adjustment will be made for the number of days under NIV support, baseline D-Dimer level and age. For the IMV patient cohort, adjustment will be made for the baseline WHO value, baseline D-Dimer level and age.

For the primary analysis of the key secondary endpoints, the delta method and average marginal effect method will be used to calculate the risk differences, the 95% confidence intervals and p-values. Adjustment will be made for the same set of default covariates as in the primary analysis of the primary endpoint.

In line with the primary and key secondary objectives of the statistical analysis, a confirmatory hierarchical testing procedure will be applied for the following set of hypotheses, in the NIV patient cohort, in the following order:-

H0_1:

The null hypothesis to be tested for the primary endpoint in the NIV patient cohort is that the hazard ratio between alteplase and SOC alone equals 1 for all $t > 0$. The alternative hypothesis is that the hazard ratio between alteplase and SOC alone is not equal to 1 for all $t > 0$. Superiority will be declared if the hazard ratio between alteplase and SOC alone is significantly greater than 1 at the two-sided type I error level alpha=5%.

H0_2:

The null hypothesis to be tested for the key secondary endpoint 'Treatment failure at Day 28' in the NIV patient cohort is that the risk difference between alteplase and SOC alone equals 0. The alternative hypothesis is that the risk difference between alteplase and SOC alone is not equal to 0. Superiority will be declared if the risk difference between alteplase and SOC alone is significantly less than 0 at the two-sided type I error level alpha=5%.

H0_3:

The null hypothesis to be tested for the key secondary endpoint 'All cause mortality at Day 28' in the NIV patient cohort is that the risk difference between alteplase and SOC alone equals 0. The alternative hypothesis is that the risk difference between alteplase and SOC alone is not equal to 0. Superiority will be declared if the risk difference between alteplase and SOC alone is significantly less than 0 at the two-sided type I error level alpha=5%.

In the first step, the primary endpoint hypothesis (H0_1) will be tested at the 2-sided type I error level of alpha=5%. If the null hypothesis (H0_1) is rejected, the key secondary endpoint hypothesis (H0_2) based on the endpoint Treatment failure at Day 28 will then be tested in a second step, again at alpha=5%. If the null hypothesis (H0_2) is rejected, the remaining key secondary endpoint hypothesis (H0_3) based on the endpoint all cause mortality at Day 28 will then be tested in a third step, again at alpha=5%.

7.2 PLANNED ANALYSES

7.2.1 General considerations

With regards to each efficacy and safety endpoint, the term "baseline" refers to the last observed measurement prior to randomisation for all patients.

The statistical analysis will be based on the following populations:

The Randomised Set (RS) will consist of all randomised patients.

The Full Analysis Set (FAS) will consist of all randomised patients with at least one baseline and one post baseline assessment relating to the primary endpoint of interest - refer to [Section 2.1.2](#) for primary endpoints related to Part 1 and Part 2.

The Treated Set (TS) will consist of all patients who were randomised and, for patients in the alteplase groups, treated with at least one dose of trial drug.

Per Protocol Set (PPS) will consist of all patients in FAS who were without important protocol deviations (IPDs) for efficacy. The definition of IPDs will be specified in the Trial Statistical Analysis Plan (TSAP) but this PPS will only be determined for Part 2.

All endpoints will be presented for Parts 1 and Part 2 separately, and at the end of Part 2 most endpoints will additionally be pooled for descriptive purposes.

All analyses for all endpoints, both inferential and descriptive, including safety, will be performed on the NIV patient cohort, and the IMV patient cohort separately. This is in line with the statistical objectives of the study.

For selected endpoints, if homogeneity between the two patient cohorts is observed, combined treatment estimates will be determined using suitable meta-analysis techniques. These will be outlined in more detail in the Trial Statistical Analysis Plan.

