7.2.2 Primary endpoint analyses

For primary endpoints related to Parts 1 and 2, refer to [Section 2.1.2](#). The primary analyses will be performed on the FAS with treatment assignments as randomised.

Part 1

The primary endpoint for Part 1 will be analysed in a similar manner to Part 2, albeit in Part 1 this will be exploratory in nature, comparing alteplase dosing regimen A to SOC alone, and alteplase dosing regimen B to SOC alone.

Part 2

For the analysis of the primary endpoint of Part 2, patients that have not met the endpoint will be censored at Day 28 if they die prior to Day 28. Patients receiving bail-out therapy (as defined in [Section 4.2.2](#)) without having first met the endpoint, will be censored on the day of bail-out. This addresses a hypothetical estimand for the scenario of what would have happened had the bail-out not been administered. Since patients requiring bail-out would be expected to be those already deteriorating, this non-informative censoring could be considered a conservative approach to assessing this estimand. Patients who have not had clinical improvement by Day 28 will be censored on Day 28.

A cox proportional hazards model will be used to estimate the hazard ratio comparing alteplase to SOC alone. From this model, the 95% confidence interval and corresponding Wald p-value for this HR will be produced. In the NIV cohort, adjustment will be made for the number of days under NIV support, baseline D-Dimer level and age. For the IMV cohort, adjustment will be made for the baseline WHO value, baseline D-Dimer level and age.

The Cox proportional hazard model assumptions will be checked.

Kaplan Meier estimates will be presented for this endpoint up to Day 28.

In anticipation of the rare situation where bail-out therapy may be used, as defined in [Section 4.2.2](#), two non-confirmatory supplementary analyses will be conducted, addressing the treatment policy estimand and a composite estimand whereby bail-out represents treatment failure and thereby, by definition, precludes any response after bail-out.

In the first of these supplementary analyses, addressing the treatment policy estimand, there will be no consideration for the intake of bail-out therapy.

In the second of these supplementary analyses, addressing the composite estimand, patients receiving bail-out therapy will be censored at Day 28, rather than on the day of bail-out.

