A sensitivity analysis of the primary endpoint (main estimand) will be carried out on the PPS, in line with the primary analysis.

Following the amendment to the inclusion criteria (CTP Version 4.0), whereby the original D-Dimer level changed from ≥ 3 -ULN to \geq ULN, some additional analyses will be performed. Firstly, a sensitivity analysis will be added, similar to the primary analysis, just replacing the baseline D-Dimer status on the two levels with that on the three levels (\geq ULN to < 3 , ≥ 3 to < 5 , ≥ 5 -ULN). Secondly, a supplementary analysis will be added, similar to the primary analysis, but removing all patients with baseline D-dimer status \geq ULN to < 3 -ULN, which is according to the expanded inclusion criteria.

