5.2 SECONDARY ENDPOINTS

5.2.1 Key secondary endpoints

The two key secondary endpoints as defined in CTP Version 3 Section 2.1.3 will be analysed on the FAS, and these are both based on the daily assessment of the WHO Clinical Progression scale.

The planned analyses of the key secondary endpoints are outlined in [Section 7.5.1](#).

Treatment failure (ACM / MV) at day 28, FAS, binary endpoint

This unfavorable endpoint is met if:

- the last known status of the patient has a value of ≥ 7 on the WHO clinical progression scale, up to end of day 28, or
- vital status is dead within 28 days

ACM at day 28, FAS, binary endpoint

This unfavorable endpoint is met if:

- the last known status of the patient is 10 on the WHO clinical progression scale by the end of day 28, or
- vital status is dead within 28 days

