6.3 SUBJECT SETS ANALYSED

The subject sets as defined in CTP Version 3 Section 7 for the Randomised Set (RS), Full Analysis Set (FAS) and Treated Set (TS) will be used.

The Screened set (SCR), not outlined in the CTP Version 3, will include all patients screened.

The RS will consist of all randomised patients.

The FAS will consist of all randomised patients with at least one baseline and one post baseline assessment relating to the primary endpoint of interest. That is to say, they need to have at least one assessment post baseline on the 11-point WHO Clinical Progression Scale.

The TS will consist of all patients who were randomised and, for patients in the alteplase group, treated with at least one dose of trial drug.

[figure not shown]
Per Protocol Set (PPS) will consist of all patients in FAS who were without important protocol deviations (IPDs) for efficacy, as outlined in [Table 6.2: 1](#).

The Pharmacokinetic set (PKS), not outlined in CTP Version 3, will comprise all subjects in the TS who provided at least one PK endpoint and had no important protocol violations relevant to the evaluation of PK.

[Table 6.3: 1](#) below outlines which analysis set is to be used for the various endpoints or summaries.

Table 6.3: 1 Subject sets analysed

Class of endpoint	Subject set			PPS	PKS
	SCR / RS	TS	FAS		
Primary endpoint			primary and supplementary analyses	Primary analyses	
Key secondary endpoints			x	Primary analyses	
Other secondary EFFICACY and further EFFICACY endpoints			x		
Secondary SAFETY and further SAFETY endpoints		x			
Treatment exposure		x			
Disposition	x				
Demographic/baseline		x	x	x	
Concomitant medications and compliance		x	x		
All other safety analyses		x			
PK analyses					x

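### Both key secondary confirmatory tests, Day 28 mortality among them, are run on a full analysis set that requires a post-baseline WHO score, and no all-randomised analysis is planned

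*Protocol*

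**What the plan says.** Protocol 7.2.1 defines the FAS as "all randomised patients with at least one baseline and one post baseline assessment relating to the primary endpoint of interest". Part 2 SAP 6.3 makes the condition concrete: "they need to have at least one assessment post baseline on the 11-point WHO Clinical Progression Scale".

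All three confirmatory tests use this set. For the primary endpoint, Protocol 7.2.2 says: "The primary analyses will be performed on the FAS with treatment assignments as randomised". For the other two, Part 2 SAP 5.2.1 says: "The two key secondary endpoints as defined in CTP Version 3 Section 2.1.3 will be analysed on the FAS". It labels mortality "ACM at day 28, FAS, binary endpoint".

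An all-randomised set exists: "The Randomised Set (RS) will consist of all randomised patients" (Protocol 7.2.1). Part 2 SAP Table 6.3:1 assigns it to disposition only. The other efficacy population is narrower than the FAS, not wider: "A sensitivity analysis of the primary endpoint (main estimand) will be carried out on the PPS" (Protocol 7.2.2). The SAP table extends the per-protocol set to the key secondary endpoints.

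Under Part 2 SAP 5.2.1, either key secondary endpoint is met if "vital status is dead within 28 days", with no WHO score needed. Protocol 6.2.3 asks for vital status on every patient at the last visit.

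**The concern.** A patient enters the FAS only if a WHO score is obtained after randomisation. Patients, investigators and site staff all know the allocation (Protocol 3.1 and 4.1.5.1), so early withdrawal and early data capture can differ by arm. A set conditioned on a post-randomisation observation no longer has the full protection of randomisation.

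The condition is hardest to justify for mortality. The endpoint can be settled without any WHO score, so the rule can discard a patient whose Day 28 outcome is on file. The standard-of-care (SOC) arm has about 70 NIV patients, and neither key secondary test has an all-randomised analysis to show whether exclusions mattered.

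**Working it through.** **Inputs.** From Protocol 7.5: 140 alteplase and 70 SOC patients in the NIV cohort; two-sided 5%; hazard ratio 2.0 with 50% and 30% events (H0_1); treatment failure 20% and 40% (H0_2); mortality 9% and 25% (H0_3). The number of patients without a post-baseline score is not given, so every exclusion count below is an assumption.

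**Step 1: the plan's own power, with all 210 patients.**
- H0_1: events = 0.30 × 70 + 0.50 × 140 = 91. Power = Φ(√(91 × 2/3 × 1/3) × ln 2 − 1.96) = Φ(1.157) = 87.6%.
- H0_2: pooled rate 56/210 = 0.267; standard error 0.0647 under the null and 0.0676 under the alternative. Power = Φ((0.20 − 1.96 × 0.0647)/0.0676) = 86.0%.
- H0_3: pooled rate 30.1/210 = 0.143; standard errors 0.0513 and 0.0571. Power = Φ((0.16 − 1.96 × 0.0513)/0.0571) = 85.1%.

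These match the stated 85% to 90% for the first two tests and 85% for the third. The sample size is sound, and it makes no allowance for patients outside the FAS.

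**Step 2: exclusions unrelated to arm or outcome.** Losing 2% gives power of 87.0%, 85.4% and 84.4%. Losing 5% gives 86.0%, 84.3% and 83.4%. The cost is below 2 points, so power is not the issue.

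**Step 3: who can fall outside the FAS.**

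| Randomised NIV patient | In FAS? | Day 28 outcome | Effect of the rule |
|---|---|---|---|
| Any later WHO score, including score 10 for death | Yes | As recorded | None |
| Early death, no later score entered | No | Dead, from vital status | Removes a death and a treatment failure; removes from the Cox model a patient otherwise censored at Day 28 |
| Immediate withdrawal, vital status obtained | No | Alive or dead known; if alive, ventilation unknown | Changes both binary denominators; almost nothing in the Cox model |
| Immediate withdrawal, vital status not obtained | No | Unknown | As above, and a missing-outcome rule is needed |

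The Cox entries follow from SAP Table 5.1:1. A withdrawal is censored on leaving, so someone censored before the first event is in no risk set.

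**Step 4: one selective exclusion in a borderline result.** Unadjusted Wald risk difference for mortality, chosen for illustration:
- All randomised: 20/140 − 18/70 = 14.3% − 25.7% = −11.4 points; SE 6.00; 95% CI −23.2 to 0.3; p = 0.057.
- One alteplase death with no post-baseline score: 19/139 − 18/70 = −12.0 points; SE 5.98; 95% CI −23.8 to −0.3; p = 0.044.

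**Step 5: bias when there is no true effect.** Let mortality be 25% in both arms, so 35 of 140 alteplase patients die, and let k of those deaths be missing from the FAS. Bias = (35 − k)/(140 − k) − 0.25. Chance of a false claim for alteplase ≈ Φ(|bias|/SE − 1.96), nominally 2.5%.

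| k | Bias (points) | False-claim chance |
|---|---|---|
| 1 | −0.5 | 3.0% |
| 2 | −1.1 | 3.7% |
| 3 | −1.6 | 4.5% |
| 5 | −2.8 | 6.4% |

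This takes H0_3 alone, without the protection of the two tests before it in the hierarchy.

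**Step 6: treatment failure in survivors.** Vital status does not show ventilation. A living NIV patient with no later score has baseline WHO 6 as last known status, which is below the threshold of 7 and so counts as success by default. Each such patient is worth 1/70 = 1.4 points in SOC, or 1/140 = 0.7 points in alteplase, between best and worst case. Part 1 SAP 5.2.2 had stated rules for unknown status; Part 2 SAP 5.2.1 has none.

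**The case against.** Exclusions should be rare. WHO scores are recorded daily in hospital, with the last value of each day kept (Protocol flow chart, footnote 11), so one end-of-Day-1 score admits a patient. Death is itself score 10 (Protocol 5.1.1). The FAS requires no dose and is analysed as randomised, so it is not a treated-only set. The SAP describes withdrawal of consent as unlikely, and disposition is reported on all randomised patients, so gross early loss would be visible. All of this stands, and it limits the expected size. It does not supply a reason for the rule: if exclusions are few, an all-randomised analysis costs almost nothing.

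A reader might infer that SOC patients who learn their allocation and leave would bias the primary hazard ratio. The documents do not support that, because such patients are censored at withdrawal and would contribute almost nothing even if kept.

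A reader might also take large shifts in SOC mortality as likely. Starting from 17.5 of 70, dropping 3 gives 14.5/67 = 21.6% to 17.5/67 = 26.1%, and dropping 5 gives 12.5/65 = 19.2% to 17.5/65 = 26.9%. The low ends need every excluded patient to have died without a score 10, the high ends need all to have survived, and nothing in the documents points to 3 or 5 such patients.

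Finally, vital status may be missing after consent is withdrawn. Protocol 6.2.3 asks for it on all patients, but 3.3.4.2, which deals with consent withdrawal, requires it only after premature treatment discontinuation. Changing the analysis set is therefore not enough by itself.

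**Conclusion.** The point holds for the two binary key secondary endpoints. The rule can remove randomised patients with known Day 28 outcomes, unevenly by arm, and no planned analysis would show the effect. It carries to the primary endpoint only through early deaths with no recorded score, who would otherwise stay at risk to Day 28.

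The likely size is small. Random loss costs under 2 points of power at an assumed 5%. The exposure is selective loss: one missing alteplase death can move a borderline mortality result across 5%. Steps 4 and 5 rest on assumed counts and an unadjusted Wald comparison, whereas the plan uses covariate-adjusted logistic regression. They show sensitivity and do not forecast what will happen.

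**What to change.** 1. Run both key secondary tests on all randomised NIV patients, as randomised. Do the same for the primary endpoint for consistency, with deaths censored at Day 28 and withdrawals at withdrawal, as the SAP already states.
2. Use vital status for mortality, with a stated rule where it is unknown at Day 28.
3. For treatment failure, count deaths from vital status. State an explicit rule for survivors with no post-baseline WHO score or with unknown Day 28 status, with a best-case and worst-case range, so that baseline WHO 6 does not become success by default.
4. Keep the FAS as a sensitivity analysis, and report exclusions from it by arm with reasons.

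No new data collection is needed. The cost is a little extra analysis and an imputation rule that will probably affect few patients. The Part 2 SAP still cites protocol Version 3, while Protocol 7.2.2 refers to Version 4.0, so the change can be made when the SAP is updated.

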7.2.2 Primary endpoint analyses

For primary endpoints related to Parts 1 and 2, refer to [Section 2.1.2](#). The primary analyses will be performed on the FAS with treatment assignments as randomised.

Part 1

The primary endpoint for Part 1 will be analysed in a similar manner to Part 2, albeit in Part 1 this will be exploratory in nature, comparing alteplase dosing regimen A to SOC alone, and alteplase dosing regimen B to SOC alone.

Part 2

For the analysis of the primary endpoint of Part 2, patients that have not met the endpoint will be censored at Day 28 if they die prior to Day 28. Patients receiving bail-out therapy (as defined in [Section 4.2.2](#)) without having first met the endpoint, will be censored on the day of bail-out. This addresses a hypothetical estimand for the scenario of what would have happened had the bail-out not been administered. Since patients requiring bail-out would be expected to be those already deteriorating, this non-informative censoring could be considered a conservative approach to assessing this estimand. Patients who have not had clinical improvement by Day 28 will be censored on Day 28.

A cox proportional hazards model will be used to estimate the hazard ratio comparing alteplase to SOC alone. From this model, the 95% confidence interval and corresponding Wald p-value for this HR will be produced. In the NIV cohort, adjustment will be made for the number of days under NIV support, baseline D-Dimer level and age. For the IMV cohort, adjustment will be made for the baseline WHO value, baseline D-Dimer level and age.

The Cox proportional hazard model assumptions will be checked.

Kaplan Meier estimates will be presented for this endpoint up to Day 28.

In anticipation of the rare situation where bail-out therapy may be used, as defined in [Section 4.2.2](#), two non-confirmatory supplementary analyses will be conducted, addressing the treatment policy estimand and a composite estimand whereby bail-out represents treatment failure and thereby, by definition, precludes any response after bail-out.

In the first of these supplementary analyses, addressing the treatment policy estimand, there will be no consideration for the intake of bail-out therapy.

In the second of these supplementary analyses, addressing the composite estimand, patients receiving bail-out therapy will be censored at Day 28, rather than on the day of bail-out.

A sensitivity analysis of the primary endpoint (main estimand) will be carried out on the PPS, in line with the primary analysis.

Following the amendment to the inclusion criteria (CTP Version 4.0), whereby the original D-Dimer level changed from ≥ 3 -ULN to \geq ULN, some additional analyses will be performed. Firstly, a sensitivity analysis will be added, similar to the primary analysis, just replacing the baseline D-Dimer status on the two levels with that on the three levels (\geq ULN to < 3 , ≥ 3 to < 5 , ≥ 5 -ULN). Secondly, a supplementary analysis will be added, similar to the primary analysis, but removing all patients with baseline D-dimer status \geq ULN to < 3 -ULN, which is according to the expanded inclusion criteria.

